In an exploratory study (study 1) our group evaluated a commercial procedure (the combined use of acute flumazenil and six weeks of gabapentin) being marketed for alcohol dependence (Anton, 2009). While initially agnostic about the utility of this approach, it provided the opportunity to explore the use of gabapentin in a structured fashion with the a priori hypothesis that this treatment would work, if at all, only in those with pre-treatment alcohol withdrawal symptoms. The theory underlying the use of IV flumazenil was that 1) it has been shown in a few, but not all, studies to ameliorate AW symptoms and 2) that it reversed the chronic effect of alcohol on GABA-A receptors (Biggio, 2007; Sanna, 2003) allowing them to be more responsive to GABA signaling. Since gabapentin had been shown previously to be useful for the treatment of AW (Myrick, 2009), and as it purportedly normalizes GABA/glutamate balance/tone in the brain, it was hypothesized to work in conjunction with flumazenil to "reset" and "maintain" normal GABA and glutamate tone resulting in less craving and relapse. Armed with this information, we randomized 60 alcohol dependent individuals in a double blind fashion to receive either active flumazenil infusions (2 consecutive days) and gabapentin up to 1200 mg/day or their matching placebos for approximately six weeks. Individuals who drank up to 72 hours prior to randomization were evaluated for alcohol withdrawal using the Clinical Institute Withdrawal Assessment – Revised (CIWA-Ar) (Sullivan, 1989) and urn randomized to the medication groups based on a CIWA-Ar score (below or ≥ 7), *with only 3 people having scores of 10 or more*. Participants were assessed for alcohol withdrawal on the first two days of treatment and drinking was assessed weekly by the timeline follow-back calendar method, with %CDT (a marker of relapse drinking) measured at baseline, week-3, and end of study. We found a significant ($p= 0.021$) effect favoring active treatment in reducing CIWA-Ar scores in the first two days of treatment. Importantly, we found no main effects of medication treatment on any drinking measure but a significant interaction of medication group by pre-randomization AW score, such that percent days abstinent ($p= 0.0006$), percent of individuals completely abstinent ($p=0.002$), time to first heavy drinking day ($p= 0.06$) and %CDT ($p=0.001$) all favored the active medication group in those with high pre-randomization CIWA-Ar scores (about 20% of subjects). Findings were similar when expanding and comparing those with and without a positive DSM-IV AW item (43% of subjects) (see Figure 1). The odds ratio for DSM-IV AW positive individuals not relapsing when treated with active medication vs. placebo was 3.2 (95% CI 1.4 - 7.4). Also, while there was more baseline drinking in those who were DSM-IV AW positive, co-varying various baseline drinking and severity (ADS, OCDS) measures did not impact the significance of the active medication vs.

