A statistical power calculation was conducted using data from our past two studies (background section) using the treatment effect in subjects with a DSM-IV history of AW on the PSNHDD outcome variable. With 45 subjects per medication group (total N=90) the power to detect the gabapentin treatment effect on PSHDD is between .83 (study 1 calculation) and .98 (study 2 calculation). While significant covariate effects in our earlier studies have not been observed with this outcome variable, additional power analysis using Monte Carlo simulation (n=500) in the presence of covariates modeled, (e.g. pretrial drinking, OCDS, ADS, etc.) on our previous studies was conducted. Power values comparable to those in the simpler analysis were found in all cases ranging from .81 to .87 (study 1) to .95 to .99 (study 2).

The statistical power calculation for gabapentin's effect on brain glutamate change from baseline to week-3 is based on the work of Umhau (2010), the study design closest to our own, where an acamprosate-induced change in brain glutamate levels (vs. placebo) was detected with an effect size of .95. *The power to detect a similar gabapentin vs. placebo difference in the current proposal with an n=45/group is in excess of .99 with the ability to detect an effect size as low as $d = .6$ with power of .8. Since the reported effect of gabapentin on GABA is quite large (Cai, 2012; Kuzniecky, 2002; Petroff, 1996; Petroff, 2000) the power to detect a gabapentin vs. placebo difference with an n=45/group is in excess of .9. Given this large statistical power, an expected maximal 10% attrition due to inadequate scans should not materially affect our ability to detect a medication effect on glutamate or GABA. Additionally, there is likely to be sufficient variation in both medication response and brain glutamate/GABA level change to allow acceptable use of a mediation analysis to examine the effect of this glutamate/GABA change on treatment response.*

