Power has not been calculated for the exploratory genetic analyses. The genetic SNP's we have chosen to explore are not only indicated by the literature but also, importantly, have a reasonable genotypic distribution. Given our past work and HapMap data (see Preliminary Data section) we expect the distribution of both the *GABRA2* and *GM8* allele frequencies to be about 60:40 with not much difference between Euro-Caucasians and African Americans. This should provide a good balance between treatment groups. Modifier effects are likely to be observable if the effect size is moderate to large. In any case, this data will allow more appropriate power calculations for subsequent studies. Effects of genetic variation on brain glutamate/GABA are unknown and completely novel but as a main effect with 90 subjects (even accounting for drop-outs or unusable scans) the power to detect a gene by analyte effect should be sufficient if clinically meaningful.

Data Analysis Plan: *The PSNHDD (with baseline percent heavy drinking days as a covariate) will be analyzed with a multiple logistic regression with indicator coding medication group as the primary independent variable. All hypotheses (primary, secondary) will be assessed with likelihood ratios. Other possible pre-randomization variables, e.g. sex, smoking status, ADS score, pre-randomization CIWA-Ar score, etc. will be evaluated as possible covariates in the final analysis. Missing data (assuming monotonicity) will be imputed as heavy drinking days. In addition, the relapse time-course will be analyzed by GEE techniques for the full treatment X time factorial design. Secondary outcome variables, e.g. other drinking variables, OCDS, POMS, PSQ index, MES and biomarkers (%dCDT and GGT), will be analyzed as either mixed models (SAS PROC MIXED) or in GEE analyses (SAS GENMOD) depending upon the nature of the variable (parametric or categorical).*

Change in glutamate and GABA levels will be analyzed as a mixed model (SAS PROC MIXED) with time as a within subject variable and medication group as between subject variables. Significant interactions will be interpreted with simple effects and main effects will be assessed in the absence of the interaction. If sex and smoking status (reported by some to effect brain GABA levels), or pre-randomization CIWA-Ar score are found to significantly influence glutamate or GABA levels, or if their inclusion reduces residual variance, they will be included in the model as covariates.

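### The stated primary-endpoint power of .83 and .98 at 45 per group is not reached at two-sided .05 from the odds ratios the plan prints, and .98 is the less supportable of the two

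*Combined protocol and SAP*

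**What the plan says.** The section Outcome Variables and Power Analyses gives the source of the calculation: "A statistical power calculation was conducted using data from our past two studies (background section"). The effect used is the one in subjects with a DSM-IV history of AW, and the outcome is the percent of subjects with no heavy drinking days (PSNHDD). With 45 per group, "the power to detect the gabapentin treatment effect on PSHDD is between .83 (study 1 calculation) and .98 (study 2 calculation").

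The same paragraph then reports simulations with covariates, "ranging from .81 to .87 (study 1) to .95 to .99 (study 2"), and introduces them this way: "Power values comparable to those in the simpler analysis were found in all cases". So .83 and .98 belong to the simpler, unadjusted comparison. No alpha or sidedness is printed with them.

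In Preliminary Data Supporting Significance, two AW-positive effects appear in the text:

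- **Study 1:** the odds ratio for AW-positive "individuals not relapsing when treated with active medication vs. placebo was 3.2 (95% CI 1.4 - 7.4").
- **Study 2:** the odds ratio for having no heavy drinking day is 4.4, with a 95% CI of 2.4 to 7.9 and p = 0.017.

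The Data Analysis Plan sets the primary model: "The PSNHDD (with baseline percent heavy drinking days as a covariate) will be analyzed with a multiple logistic regression".

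**The concern.** The power paragraph points to the background section for its effect sizes. Putting the printed odds ratios into a standard two-group calculation does not return the stated power. The placebo rate is not in the readable text, but it cannot close the gap: for a fixed odds ratio and sample size, power has a maximum over placebo rates, and both maxima lie below the stated values.

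This paragraph is the justification for N=90 on the primary endpoint. If true power at the study 1 effect is below .80 rather than .83, or power at the study 2 effect is well below .98, a non-significant result would be weaker evidence against gabapentin than a reader of the plan would believe.

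**Working it through.** **Inputs from the plan.** n = 45 per group; odds ratios (OR) 3.2 and 4.4; stated power .83 and .98; study 2 p = .017 and 95% CI 2.4 to 7.9; study 2 had 150 subjects in three arms, 56% AW-positive.

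**Assumptions.** Alpha .05, tried two-sided and one-sided. The placebo rate p0 was scanned from .02 to .895 and the best case kept, which favours the plan. The active rate is p1 = OR·p0/(1 − p0 + OR·p0).

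**1. Attempt to reproduce .83 (OR 3.2).** The best p0 is about .36, giving p1 = .643 and a difference of .283.

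- Unpooled SE = √[(.36×.64 + .643×.357)/45] = .101. Power = Φ(.283/.101 − 1.96) = Φ(.84) = .80.
- Pooled null SE = √[2×.50×.50/45] = .105. Power = Φ[(.283 − 1.96×.105)/.101] = .775.
- Exact enumeration of all 46×46 outcomes (likelihood-ratio and Pearson tests agree): .764.

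**2. Attempt to reproduce .98 (OR 4.4).** The best p0 is about .325, giving p1 = .679 and a difference of .354.

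- Unpooled SE = .0986. Power = Φ(.354/.0986 − 1.96) = Φ(1.63) = .949.
- Pooled: .933. Exact: .926.

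**3. Maxima over all placebo rates.**

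| OR | Stated | Two-sided .05: exact / pooled / unpooled | One-sided .05: exact / pooled / unpooled |
|---|---|---|---|
| 3.2 | .83 | .764 / .775 / .799 | .874 / .861 / .876 |
| 4.4 | .98 | .926 / .933 / .949 | .970 / .967 / .974 |

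Neither stated figure is reached two-sided. One-sided, .83 is reached but .98 is not. Away from the best placebo rate, power falls. At assumed rates of .10, .20 and .30, exact two-sided power is .54, .72 and .76 for OR 3.2, and .79, .91 and .93 for OR 4.4.

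**4. Size of the gap.** At two-sided .05 and the best placebo rate, the stated power would need odds ratios of about 3.35 to 3.55 (for .83) and 5.2 to 5.8 (for .98). These show scale only.

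**5. A second route to study 2 power, without the odds ratio.** A two-sided p = .017 gives z = 2.39. Assume equal arms: 150/3 = 50 per arm, and 56% of 50 = 28 AW-positive. Scaling to 45 per group: 2.39 × √(45/28) = 3.03. Power = Φ(3.03 − 1.96) = .86 two-sided, and Φ(3.03 − 1.645) = .92 one-sided. Neither is near .98.

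**6. Consistency of the study 2 result.**

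- From the CI: SE(log OR) = ln(7.9/2.4)/(2×1.96) = .304, so z = ln(4.4)/.304 = 4.87, or p of about 10⁻⁶.
- From the p-value: z = 2.39, so SE = 1.482/2.39 = .62, and the matching 95% CI would be about 1.3 to 14.9.

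The printed CI and the printed p-value cannot both describe the same comparison.

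**The case against.** **The inputs are inferred.** The plan says that data from the two studies were used, not that the printed odds ratios were. The study 1 odds ratio is worded as not relapsing and may come from a different model. Figures 1 and 2, not shown in this copy, may hold the arm proportions. All of this stands, and it protects the .83. Taking about 13 AW-positive subjects per arm in study 1 (43% of 60 is about 26), an illustrative 4/13 against 8/13 has an odds ratio of 3.6 and exact two-sided power of .836 at 45 per group. It protects the .98 much less: the study 2 odds ratio is printed for the no-heavy-drinking-day outcome itself, and the p-value gives a separate route that also falls short.

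**The primary model is covariate-adjusted, so an unadjusted ceiling may not bind.** This is partly right. In simulations that read the odds ratios as marginal and used one covariate with an assumed odds ratio of 1.65, 2.12 or 2.72 per SD, adjusted power was .81, .82 and .86 for study 1 and .94, .96 and .96 for study 2. A strong covariate can therefore bring study 1 to .83; .98 was not reached. With an uninformative covariate the values were .77 and .92. The stated .83 and .98 are in any case the unadjusted figures, and the plan reports that "significant covariate effects in our earlier studies have not been observed with this outcome variable", although non-significance in small subgroups does not show that covariates carry no information.

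**Stronger readings that the documents do not support.**

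- *One paragraph mixes one-sided and two-sided tests.* The glutamate statement, "the ability to detect an effect size as low as $d = .6$ with power of .8", does fit two-sided .05 (.804, against .881 one-sided). But a one-sided primary calculation is only one possible explanation of .83, so mixed sidedness is conjecture.
- *The printed CIs are really the odds ratio plus or minus one SE.* Nothing in the text says so. What is shown is that the study 2 CI and p-value disagree.

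**Conclusion.** The point holds in conditional form. On the only AW-positive effects printed, unadjusted power with 45 per group at two-sided .05 is at most about .76 to .80 for study 1 and .93 to .95 for study 2, against .83 and .98 stated. Measured against the most generous formula, the shortfall is about three points in each case; it is larger with the exact test or a less favourable placebo rate.

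The two figures differ in standing. The .83 is unconfirmed but not proven wrong. The .98 is not obtained from OR 4.4 under either sidedness, and the printed p-value projects to about .86. That projection assumes about 28 AW-positive subjects per arm and a two-sided p-value. The inconsistency between the study 2 CI and p-value needs no assumption about the power inputs.

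A reader might infer that the trial is underpowered or that N=90 is wrong. The documents do not support that: the actual arm proportions may differ from what the printed odds ratios imply, and an informative covariate could raise power in the adjusted primary model.

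**What to change.** Keep N=90, the endpoint and the analysis.

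1. Recompute the primary-endpoint power at two-sided .05 from the actual AW-positive arm proportions in the two studies, and restate it with those proportions beside it.
2. If the printed odds ratios are the inputs, state unadjusted power as at most about .76 to .80 (study 1) and .93 to .95 (study 2).
3. Rerun the covariate simulations on the same inputs and report the adjusted power separately.
4. Correct whichever of the study 2 CI and p-value is wrong.

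The cost is a revised paragraph, one rerun simulation and one corrected figure in the background section. The downside is a slightly less favourable stated power.

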these criteria based on data from our 4 recent clinical trials containing a total of almost 400 subjects. A CIWA-Ar score of 10 or more at any time during screening (5% of AW SCID positives based on recent studies), indicating the need for a more aggressive medical detoxification (Mayo-Smith, 1997; Saitz, 1998), will be exclusionary and we will refer the subject for clinical care and/or provide short-term benzodiazepine (lorazepam) until further care can be arranged. We feel that this is a fair compromise between appropriate subject selection, ethical treatment of subjects, and scientific integrity (referring individuals for clinical care and not including participants taking benzodiazepines which might compromise efficacy measures, GABA/glutamate levels, or interpretation of gabapentin response).

Study subjects will be asked to come into the clinic at least 2 times prior to randomization (with breathalyzer, CIWA-Ar, and urine EtG collected). During this time a full SCID, other questionnaires, a physical history and exam will be done. Subjects who maintain sobriety for at least 3 days will undergo a mass spectroscopy scan (¹H-MRS for glutamate and GABA) immediately before receiving the first MM session and first dose of study medication. We chose 3 days of sobriety based on our past results from previous work (Anton 2011) but not too long (no longer than 7 days) as to effect potential gabapentin efficacy measurement and/or GABA/glutamate levels. If they cannot maintain sobriety, or have a positive EtG on day 3 of abstinence, they will be given an additional chance to make the abstinence criteria before being excluded. For smokers, time of the last cigarette will be recorded and used as a covariate in the glutamate/GABA analysis, if necessary.

Procedure for Pre-Study Evaluation:

Subjects will receive all the pre-study assessment over a several day assessment period during the pre-randomization abstinent period (sobriety days 3-7).

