Proton Magnetic Resonance Spectroscopy (¹H-MRS) for Glutamate and GABA: This will occur prior to randomization (see above) and again at week 3 (window between days 17-24) of study medication between 2-4 hours after the last gabapentin/placebo dose to standardize acute dosing effects. Subjects will be breathalyzed prior to the scan and need to be zero (or will be rescheduled ASAP), and, if smokers, the time of last cigarette will be recorded. In an ongoing trial we have found no problems with imaging (fMRI) clinical trial participants twice (baseline/week 3) – very few have to be rescheduled due to drinking and some subjects find it intriguing. Each scan takes about 60 minutes and uses the following protocol: A structural scan will be taken for ¹H-MRS voxel placement and tissue segmentation (256 sagittal slices; 1mm thick/50% gap). The ACC voxel for ¹H-MRS will be placed on midsagittal T1-weighted images, anterior to the genu of the corpus callosum, with the ventral edge of the voxel aligned with the dorsal edge of the genu and a voxel size of 3 x 2.5 x 2.5 cm³ will be selected (consistent with Umhau, 2010 and Mon, 2012). Following auto-shimming, single-voxel water-suppressed ¹H-MRS spectra will be acquired using a Point Resolved Spectroscopy (PRESS) sequence: Repetition Time (TR) = 2000ms; Echo Time (TE) = 40ms; number of averages = 256); an unsuppressed water spectrum will be co-acquired (TE = 40ms, number of averages = 16), scaled for partial volume effects and relaxation, and used as a concentration reference. This sequence has been shown to

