Only metabolites with fitting uncertainties (Cramer-Rao Lower Bound values) < 20% of SD in the LC Model output will be retained for analysis. LC Model includes standardized zero filling, Fourier transformation, and automated phase, baseline, and eddy current correction. To address variability in within-voxel tissue composition we will: 1) co-register T₁-weighted images to their scout images and correct for b₁ field bias, 2) extract and segment T₁-weighted images into partial volume maps of gray matter (GM), white matter (WM), and CSF using FMRIB Software Library (FSL) tools, 3) match the coordinates and size of the ¹H-MRS voxel with the segmented images and extract the tissue fractions within the voxel using FSL tools, 4) correct the raw values obtained from the LC model (scaled to water) for CSF and coil loading (Michaelis, 1993), and 5) calculate each participant's GM to brain matter (BM) ratio (i.e., GM:BM = GM/[GM+WM]) for use as a covariate in statistical analyses. This calculation will be made separately for each metabolite of interest because the spatial region that each metabolite is localized to is not the same due to the chemical shift artifact. The particular displacement of a given metabolite's localization region is determined by the metabolite's chemical shift divided by the product of the strength of the gradient used to localize the voxel and the gyromagnetic ratio for protons. For each metabolite, in each participant, we will match the coordinates and size of the voxel (accounting for chemical shift displacement) with the segmented images and extract the tissue fractions using FSL tools. Metabolite concentration estimates will be corrected for T₁ and T₂ relaxation effects using established literature values (Mlynarik, 2001; Wansapura, 1999) and scaled to water. Following this procedure we have produced the following example spectra:

FIGURE 3. LC Model Spectra for Glutamate

[figure not shown]
[figure not shown]

FIGURE 4. LC Model Spectra for GABA

We have run 6 healthy controls *through the PRESS MRS sequence* and found a mean (SD) glutamate, as a ratio to water, of 7.66 (1.24) or as a ratio to creatine, 1.38 (0.15). *We have run an additional 7 healthy controls through the MEGA-PRESS MRS sequence and found a mean (SD) GABA, as a ratio to water, of 1.75 (0.19). These values are consistent with published levels (where there is a range of values based on quantification method and reference analyte).*

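### The group-by-time test for glutamate and GABA is valid, but a week-3 contrast adjusted for the pre-dose level is in general more precise, and the plan should say that a group main effect is not evidence of a drug effect

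*Combined protocol and SAP*

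**What the plan says.** The Data Analysis Plan states: "Change in glutamate and GABA levels will be analyzed as a mixed model (SAS PROC MIXED) with time as a within subject variable", with medication group between subjects. It continues: "Significant interactions will be interpreted with simple effects and main effects will be assessed in the absence of the interaction".

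The first of the two scans is free of drug. The screening paragraphs of the Approach place it "immediately before receiving the first MM session and first dose of study medication", and the ¹H-MRS section says of the scans: "This will occur prior to randomization (see above) and again at week 3".

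Several covariates are named for these analyses:
- time of last cigarette, to be "used as a covariate in the glutamate/GABA analysis, if necessary" (screening paragraphs);
- the gray-matter ratio, "for use as a covariate in statistical analyses" (¹H-MRS section);
- sex, smoking status and pre-randomization CIWA-Ar, if they influence the levels, "or if their inclusion reduces residual variance, they will be included in the model as covariates" (Data Analysis Plan).

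The analyte's own pre-dose level is not among them, and no common baseline mean is specified. By contrast, the primary outcome, PSNHDD, is analysed "with baseline percent heavy drinking days as a covariate".

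Outcome Variables and Power Analyses gives, for 45 per group, power above .99 at d = .95 for glutamate and .8 at d = .6. It allows for up to 10% loss from inadequate scans.

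**The concern.** A group difference in a scan taken before randomization can only be chance. The planned model nevertheless treats that scan as an outcome with its own group difference. Two consequences follow.

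**Precision.** Differencing subtracts the whole pre-dose value, whatever its relation to the week-3 value. Adjustment subtracts only the part that predicts week 3, so its residual variance is no larger and is usually smaller. The plan already accepts covariates that reduce residual variance, and the strongest candidate is likely to be the one it leaves out. The background section also reports that the largest GABA increases on gabapentin occurred at the lowest baseline levels, so baseline may well be related to change.

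**Interpretation.** A group main effect averages a drug-free scan with an on-drug scan. Its expected value is half the week-3 drug effect, and it also carries any chance pre-dose imbalance. If it were taken as evidence of a drug effect after a null interaction, each analyte would have two chances of a false positive.

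At stake is the sensitivity and clarity of the mechanistic aim. The primary PSNHDD analysis and the mediation regression on difference scores are not affected.

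**Working it through.** **Inputs from the documents:** 45 per group; d = .95 and d = .6, both for change from baseline to week 3; up to 10% scan loss, so 40 to 41 per group.

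**Assumed:** two-sided .05 (not stated for these tests); d in SDs of change (the SD used is not stated); test-retest correlation ρ from .3 to .9; week-3/baseline SD ratio k, first 1, then .75 to 1.5.

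**1. The plan's own figures.** With two scans and complete data, group-by-time equals a t-test on change. The noncentrality is d√(n/2) = .6 × √22.5 = 2.85 with 88 df, and power is .804. At d = .95 power is .994. Both match the plan. One-sided .05 would give about .885 at d = .6 (normal approximation), which supports the two-sided reading.

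**2. Adjusted test, equal SDs.** The variance of change is 2σ²(1−ρ). The residual variance after adjustment is σ²(1−ρ²). The ratio of adjusted to change variance is (1+ρ)/2, so d becomes d√(2/(1+ρ)), with one df fewer. At ρ = .5, .6 × 1.155 = .693, the noncentrality is 3.29, and power is .901.

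| ρ | Effective d | Power, 45 per group | Power, 40 per group |
|---|---|---|---|
| group-by-time | .600 | .804 | .755 |
| adjusted, .3 | .744 | .937 | .908 |
| adjusted, .5 | .693 | .901 | .864 |
| adjusted, .7 | .651 | .863 | .820 |
| adjusted, .8 | .632 | .843 | .798 |
| adjusted, .9 | .616 | .823 | .776 |

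At 40.5 per group, exactly 10% loss, the planned test has power .760. Simulation with 45 per group (40,000 trials per setting) gave .936, .899 and .841 for the adjusted test at ρ = .3, .5 and .8.

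**3. Unequal SDs.** The multiplier on d becomes √(1+k²−2ρk) / (k√(1−ρ²)). It equals 1, so there is no gain, when ρk = 1. With 45 per group and d = .6:
- k = 1.25: .846 (ρ = .5), .811 (.7), .804 (.8);
- k = 1.5: .818 (ρ = .5), .804 (.7);
- k = .75: .96 to .99 for ρ from .3 to .9.

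**4. Other scales and effects.** If d is in SDs of level (k = 1), the planned test has power .66, .80, .95 and .99 at ρ = .3, .5, .7 and .8, against .84, .90, .98 and .997 adjusted. At d = .95 in SDs of change, the adjusted power is .994 or more, against .994 as planned.

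**5. Group main effect counted as a drug effect.** With equal SDs, the change and the two-scan mean are uncorrelated. The chance that at least one test is significant with no drug effect is therefore about 1 − .95² = .0975. Simulation gave about 9.7% with t-tests and equal SDs, 8.9 to 9.7% with k of .75, 1.25 and 1.5, and 9.5 to 10.4% with likelihood-ratio tests. The adjusted test alone stayed at about 5%.

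The extra error buys nothing. At d = .6 and ρ = .3, .5 and .8, counting either test gave power .911, .876 and .836, against .936, .899 and .841 for the single adjusted test.

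**The case against.** The strongest reply is that nothing here is an error. The analysis is framed as change throughout: in the power section, in the opening words of the glutamate/GABA paragraph, and in the mediation regression. A reader might infer that the plan ignores the pre-dose scan or that its test is invalid. The documents do not support that, because differencing uses every complete pair and removes chance baseline differences. This part of the reply stands: the issue is efficiency.

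Secondly, the size of the gain rests on a correlation, an SD ratio and a unit for d that the documents do not give. It also shrinks to almost nothing at the planned d = .95, and the GABA effect is expected to be large. This stands too. But the plan itself quotes d = .6 as detectable with power .8, and its own 10% scan loss takes that below .8. Moreover, the .95 comes from acamprosate, and the background section reports that the only gabapentin study of glutamate, a single-dose one, found no significant effect.

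Thirdly, assessing main effects is ordinary factorial wording, and a time main effect answers a stated interest in change during early abstinence. A reader might infer that the plan would declare a drug effect from a group main effect. It does not say so. The 9.7% is conditional on that reading, which the text leaves open.

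Finally, adjustment is not entirely free. A week-3 model with the pre-dose level as covariate drops subjects whose pre-dose scan is unusable, whereas the planned mixed model can keep them. That is correct, and it favours the common-baseline version.

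**Conclusion.** The point holds as an improvement in efficiency plus a clarification. The planned group-by-time test is valid. A week-3 contrast that uses the pre-dose level is in large samples never less precise, and usually more so.

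Under two-sided .05, d = .6 in SDs of change, 45 per group and equal SDs, power rises from .80 to between .82 (ρ = .9) and .94 (ρ = .3). With 40 per group it rises from about .76 to between .78 and .91. These ranges are conditional on assumed values and should not be quoted as the trial's power. Over the SD ratios examined, the result runs from no gain to .99, and at d = .95 the question hardly matters.

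The false-positive figure of about 9.7% per analyte applies only if a group main effect were counted as a drug effect.

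**What to change.** For each analyte, name one test of drug effect: the week-3 group contrast from a two-scan mixed model in which both groups share a common baseline mean. This keeps subjects with only one usable scan. The alternative is the week-3 level by group with the pre-dose level as covariate; its small downside is losing subjects whose pre-dose scan is unusable.

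Add one sentence that a group main effect is not evidence of a drug effect, and that a time main effect may be reported descriptively. If the present model is kept, the minimum is a sentence that only group-by-time counts as evidence of a drug effect. State the alpha for these tests in the same place.

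The cost is two or three sentences in the Data Analysis Plan and, with the covariate version, one degree of freedom. Both scans are already planned, so no subjects or scans are added. The mediation regression can keep its difference scores; the text should then note that the drug-effect estimate and the mediator are on different metrics.
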